10.5.6 Subgroup and Adjusted Analyses for Primary Endpoints

As an explanatory analysis, subgroup analyses of the primary outcomes may be conducted to explore whether estimated treatment effects vary significantly between subcategories of trial subjects, including, but not limited to, bacteriophage susceptibility and presence of co-infection with other organisms recovered on sputum cultures collected during the study period. In addition, the primary endpoints will adjust for pre-randomization variables, which might reasonably be expected to be predictive of favorable outcomes.

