#### 3.3.2. Baseline

Baseline for all variables will be defined as the last measurement/laboratory value collected prior to dosing during the Baseline/Dosing Visit 2 (Day 1), unless otherwise noted.

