## 6.4. Covariates and Subgroups

An exploratory analysis of the primary outcomes will be conducted to explore whether estimated treatment effects vary significantly between subcategories of trial subjects. Bacteriophage susceptibility will be the only pre-specified subgroup analyzed, however exploratory analyses of the primary endpoints may be performed using any other subgroups of interest.

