## 8. MICROBIOLOGICAL ACTIVITY AND BENEFIT TO RISK PROFILE EVALUATION

All variables in the microbiological activity and benefit to risk profile analyses will be listed by subject. Data will be summarized by treatment group. Continuous variables will be summarized with the number of observations, mean, median, SD, quartiles, minimum, and maximum. Categorical variables will be summarized by number and percent in each category. All microbiological activity and benefit to risk profile analyses will be performed using the ITT population.

This study does not include formal hypothesis testing for any of the primary endpoints, and instead relies on CIs for conclusions of treatment effects.

All microbiological activity and benefit to risk profile tables and figures will compare all subjects receiving placebo to all subjects receiving the selected dose of IV bacteriophage chosen from the interim analysis.

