## **14. TECHNICAL DETAILS**

SAS version 9.4 or above and R versions 3.2 or above will be used to generate the tables, figures, and listings.

**15. SUMMARY OF CHANGES IN THE CONDUCT OF THE STUDY OR  
PLANNED ANALYSES**

No changes have occurred in the conduct of the study or planned analyses.

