aQ1 and Q3 represent the 25th and 75th percentiles, respectively.b95% CI (confidence interval) is calculated from a t-distribution.

**Table 21: Difference in Mean Change from Baseline in *P. aeruginosa* Total Colony Counts in Quantitative Sputum Cultures – ITT Population, Stage 2a and 2b**

[Implementation note: The 95% CI for the difference in means is computed from Welch's t-test.]

Time Point	Difference in P. aeruginosa CFU/mL Mean Change from Baseline (95% CI a )	Difference in $\log_{10}$ P. aeruginosa CFU/mL Mean Change from Baseline (95% CI a )
Day 1 Post-infusion	xx (xx.x, xx.x)	xx (xx.x, xx.x)
Day 2	xx (xx.x, xx.x)	xx (xx.x, xx.x)
Day 5	xx (xx.x, xx.x)	xx (xx.x, xx.x)
Day 8	xx (xx.x, xx.x)	xx (xx.x, xx.x)
Day 30	xx (xx.x, xx.x)	xx (xx.x, xx.x)
Maximum	xx (xx.x, xx.x)	xx (xx.x, xx.x)

Notes: Difference calculated as Placebo – IV Bacteriophage.

aThe 95% CI for the difference in means is computed from Welch's t-test.

**Table 22: Subgroup Analysis of Difference in Mean Change from Baseline in *P. aeruginosa* Total Colony Counts in Quantitative Sputum Cultures – ITT Population, Stage 2a and 2b**

[Implementation note: The following subgroups will be included in this analysis: Susceptible to bacteriophages – Yes, Susceptible to bacteriophages – Yes, Presence of Co-infection with Organism X – Yes, Presence of Co-infection with Organism X – No.]

Implementation note: The 95% CI for the difference in means is computed from Welch's t-test.]

Subgroup	Time Point	n b (%)	n p (%)	Difference in Mean Change from Baseline (95% CI a )	Difference log 10 in Mean Change from Baseline (95% CI a )
Susceptible to Bacteriophages – Yes	Day 1 Post-infusion	x (x)	x (x)	xx (xx.x, xx.x)	xx (xx.x, xx.x)
	Day 2	x (x)	x (x)	xx (xx.x, xx.x)	xx (xx.x, xx.x)
	Day 5	x (x)	x (x)	xx (xx.x, xx.x)	xx (xx.x, xx.x)
	Day 8	x (x)	x (x)	xx (xx.x, xx.x)	xx (xx.x, xx.x)
	Day 30	x (x)	x (x)	xx (xx.x, xx.x)	xx (xx.x, xx.x)
	Maximum	x (x)	x (x)	xx (xx.x, xx.x)	xx (xx.x, xx.x)
...					
Presence of Co-infection with Organism X – No	Day 1 Post-infusion	x (x)	x (x)	xx (xx.x, xx.x)	xx (xx.x, xx.x)

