The primary analysis of the DOOR and *P. aeruginosa* colony count endpoints will substitute undetectable results using the lower limit of detection of the assay at the time of data collection. A sensitivity analysis will also be conducted wherein any undetectable values are treated as missing.

[figure not shown]
[figure not shown]
The tables, figures, and listings (TFLs) from v1.0 of the SAP that are affected by the change in assumptions of the primary analysis are listed in Appendices 1-3. The tables and figures in Appendix 1 and 2 will be repeated for the sensitivity analysis with the addition of “, Sensitivity Analysis” appended to the end of the TFL titles. Additionally, figures starting with [Figure 19](#) and continuing through [Figure 24](#) will be added to the report to visualize colony counts over time from Baseline through Day 8. The affected listings in Appendix 3 will not be repeated for the sensitivity analysis results but instead include either an implementation note to mark any substituted colony count ([Listing 1](#)) or a new column for ‘Sensitivity Analysis DOOR Category’ ([Listing 2](#)).

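### The protocol says the primary endpoints will be adjusted for pre-randomization variables, but the SAP and its addendum give only unadjusted estimates and record no change; the AUC population is also stated two ways

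*Protocol*

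**What the plan says.** **Protocol.** Section 10.5.6 covers both subgroup and adjusted analyses of the primary endpoints. The subgroup part is optional: "subgroup analyses of the primary outcomes may be conducted". The adjustment part is not: "In addition, the primary endpoints will adjust for pre-randomization variables, which might reasonably be expected to be predictive of favorable outcomes". No covariate, model or effect measure follows. Protocol Table 3, introduced in 10.5.5 as the summary of all analyses, lists no adjusted analysis.

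**SAP.** Section 1 says the SAP covers every planned analysis. Section 6.4, headed for covariates and subgroups, names no covariate; it says "Bacteriophage susceptibility will be the only pre-specified subgroup analyzed". Section 6.7 rules out adjustment for site. For colony counts, the note to Table 21 says "The 95% CI for the difference in means is computed from Welch" (the t-test), and Table 24 does the same for AUC. Section 15 states: "No changes have occurred in the conduct of the study or planned analyses".

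**Addendum.** It lists the outputs "affected by the change in assumptions of the primary analysis", meaning the new handling of undetectable counts. Otherwise it keeps the SAP methods. Tables 5, 6, 11 and 12 are again Welch only.

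**AUC.** SAP 8.1.2 calculates an AUC only for subjects with no missing count from baseline through Day 30. The notes to SAP Table 23 and addendum Tables 9 and 10 define an AUC from baseline to each time point, with n counted at that time point.

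**The concern.** An analysis that the protocol says will be done has no specification, no table shell and no record of having been dropped. The SAP promises to explain departures from itself, so an omission relative to the protocol could pass without comment in the study report.

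Width matters here because SAP Section 8 says the study does no formal testing and "instead relies on CIs for conclusions of treatment effects". Baseline log10 CFU is already collected and is the obvious candidate covariate. The AUC is of absolute log10 counts, so unlike the change score it does not subtract baseline, and a chance baseline difference between arms carries into it.

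The two AUC statements give different denominators for the same rows. A subject missing only the Day 30 sample has no AUC in any row under SAP 8.1.2, but counts in the rows up to Day 8 under the table notes.

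**Working it through.** The plan gives no figure of its own to reproduce here, so the first step is textual.

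**1. Is there an adjusted estimate anywhere?**
- Grade 2 or higher AEs: difference in proportions (SAP 8.1.1, Table 45). Unadjusted.
- Change in log10 CFU, and AUC: Welch (SAP 8.1.2, Tables 21 and 24; addendum Tables 5, 6, 11 and 12). Unadjusted.
- DOOR: Wilcoxon-Mann-Whitney with the Halperin interval (SAP 8.1.3). Unadjusted.
- Subgroups (SAP 8.2.4) stratify; they do not adjust.
- Inverse probability weighting (SAP 8.1.3.1) models missing DOOR data. Its pseudocode has treatment as the only regressor, so every pair gets the same weight. In a test data set the weighted and unweighted DOOR probabilities were both 0.5441.

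**2. What would adjustment do to the Day 30 change interval?** Inputs: 20 per arm, up to 25 (Protocol 10.2). The documents give neither the baseline-to-Day 30 correlation ρ nor the ratio k = SD(Day 30)/SD(baseline), so both are assumed. In units of the baseline SD, the variance of the change score is 1 + k² − 2ρk and the ANCOVA residual variance is k²(1 − ρ²). Their difference is (1 − ρk)², which is never negative and is zero at ρ = 1/k. With N subjects in both arms,

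CI ratio (ANCOVA/Welch) = √[k²(1−ρ²)/(1+k²−2ρk) × (N−3)/(N−4)] × t(N−3)/t(N−2).

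For k = 1 the first factor reduces to (1+ρ)/2. Example, N = 40, ρ = 0.5: √(0.75 × 37/36) × 2.0262/2.0244 = 0.879.

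| N = 40 | ρ = 0.3 | 0.5 | 0.7 | 0.9 |
|---|---|---|---|---|
| k = 1.0 | 0.818 | 0.879 | 0.936 | 0.989 |
| k = 1.2 | 0.886 | 0.947 | 0.997 | 1.003 |
| k = 1.3 | 0.911 | 0.969 | 1.010 | 0.972 |
| k = 1.4 | 0.931 | 0.985 | 1.014 | 0.933 |
| k = 0.8 | 0.719 | 0.767 | 0.804 | 0.791 |

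The worst case is ρ = 1/k, where only the cost of one extra parameter remains: √(37/36) × 2.0262/2.0244 = 1.0147, about 1.5% wider. With 25 per arm and k = 1 the ratios are 0.815, 0.876, 0.932 and 0.986.

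**3. AUC.** Trapezoid weights over Day 1 pre-dose, Day 1 post-dose (taken as 2.5 h), and Days 2, 5, 8 and 30 are 0.002, 0.017, 0.067, 0.103, 0.431 and 0.379. Assume that all visits share one ρ and one SD. The correlation r of AUC with baseline is then 0.409, 0.611, 0.781 and 0.931 at ρ = 0.3, 0.5, 0.7 and 0.9. Replacing the first factor by 1 − r² gives CI ratios of 0.926, 0.803, 0.633 and 0.370 (N = 40). A baseline difference of one standard error, √(2/20) = 0.316 SD, multiplied by slopes of 0.301, 0.501, 0.701 and 0.900, moves the unadjusted time-averaged AUC difference by 0.095, 0.158, 0.222 and 0.285 SD.

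**4. AUC denominators.** Assume that each sample is missing independently with probability p. An arm of 20 then has 20(1−p)^m subjects when m samples are needed.

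| | m | p = 2% | 5% | 10% |
|---|---|---|---|---|
| SAP 8.1.2, all rows | 6 | 17.7 | 14.7 | 10.6 |
| Table note, Day 8 row: baseline and Day 8 only | 2 | 19.2 | 18.1 | 16.2 |
| Table note, Day 8 row: intermediate visits also needed | 5 | 18.1 | 15.5 | 11.8 |

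On the last reading the Day 30 row needs all six samples, so the two rules agree there.

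**The case against.** The sentence in Protocol 10.5.6 is vague, follows a sentence about exploratory subgroup work, and has no counterpart in Protocol Table 3. The change score and the DOOR reduction already subtract each subject's own baseline. Baseline log10 CFU and ANCOVA are this review's choice, made after the dose was selected on 02FEB2024. A line in Section 15 saying that no adjustment is done would resolve the inconsistency by itself. All of this stands, and it limits the weight of the point. It does not turn a stated intention to adjust into an option, or supply the missing record.

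A reader might infer that adjustment must narrow the Day 30 interval unless ρ exceeds about 0.94. That holds only for equal SDs at the two visits, which the documents do not state. Isolates are not screened for phage susceptibility before dosing, so response may vary and Day 30 SD may exceed baseline SD. At k = 1.2 and ρ = 0.7 the gain has gone.

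A reader might also take the AUC gap at Day 8 to be 1.5 to 5.6 subjects per arm. That needs the table note read as requiring only baseline and Day 8. If the trapezoid uses its intermediate visits, the gap is 0.4 to 1.2, though larger in earlier rows.

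Two technical limits also stand. Baseline is "defined as the last measurement/laboratory value collected prior to dosing", and Protocol 10.3.1 releases the randomization code at the same visit, so the count is pre-treatment but not assuredly pre-randomization. And substitution at the detection limit shrinks a true shift under either estimator. In simulation (3/32 of baselines floored, assumed shift 0.67 SD, 20 per arm, ρ from 0.3 to 0.9), both averaged about 0.56 SD. The narrower ANCOVA interval covered the true shift slightly less often (0.865–0.932 against 0.873–0.940).

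**Conclusion.** The point holds as a gap between protocol and SAP. A planned adjusted analysis of the primary endpoints is neither specified nor recorded as dropped, and the AUC population has two definitions.

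It would go too far to infer that the Welch results are invalid or that a trial decision is at risk. Protocol 10.5.5 asks for an unadjusted difference with its interval, there is no formal testing, and the only stated decision rule concerns the DOOR interval.

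For the Day 30 change the expected gain is modest and depends on assumed ρ and SD ratio: 18% to 1% narrower for ρ from 0.3 to 0.9 with equal SDs, more or less otherwise, and a loss of about 1.5% at worst. The gain is clearer for the AUC (7% to 63% under equal correlation), but the AUC is supportive. The size of the AUC denominator conflict depends on assumed missingness and on how the table note is read.

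**What to change.** 1. Keep Welch. Beside it, in SAP Tables 21 and 24 (addendum Tables 5 and 11), add an ANCOVA difference with 95% CI on the log10 scale, adjusted for baseline log10 CFU, with Day 30 as the endpoint row. Use the addendum's detection-limit substitution, and repeat in addendum Tables 6 and 12 with undetectable values treated as missing.
2. State that the pre-dose Day 1 count serves as the pre-randomization variable, and why: it precedes treatment, in a double-blind stage.
3. Label the model as specified after the interim analysis. It should be written by the blinded statistician whom Protocol 10.4.2 involves in SAP revisions, and fixed before final unblinding.
4. For the AE and DOOR endpoints, name the covariates or record in Section 15 that adjustment is not done. If no adjusted estimate is added at all, record that for all three endpoints, with the reason.
5. State one AUC rule, including whether intermediate visits are required, and use it in SAP 8.1.2, Tables 23 and 24 and addendum Tables 9 to 12.

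Cost: one model, one added column in two tables and their sensitivity versions, and a few sentences in the addendum. No new data are needed.

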10.5.7 Analysis of Exploratory Endpoints

Exploratory endpoints will be summarized by appropriate statistics. Continuous variables will be summarized by number of subjects, mean, SD, median, quartiles, minimum, and maximum values. Categorical variables will be summarized by number and percentage of subjects. Blood and sputum samples collected from the sentinel subjects in Part 1 will be used for exploratory analysis purposes. Phage PK will be analyzed using compartmental population PK models to obtain population mean estimates of clearances and volumes as well as estimates of inter-individual variability. Individual estimates of clearances and volumes will be obtained from post hoc estimates and used to estimate exposure in the central compartment and a peripheral compartment representing the sputum. Additional details regarding exploratory analysis will be included in the SAP.

10.5.8 Missing Data

The endpoints could be missing for subjects who withdraw from the trial or for other reasons. The reasons for withdrawal will be reported and compared qualitatively by arm. The effect that any missing data might have on results will be assessed via sensitivity analysis. If the pattern of missing data is different to that envisaged at the design stage, further sensitivity analyses will be provided that are tailored to the missing data pattern observed. The amount of missing data will be compared between randomized arms. The baseline characteristics of subjects with missing data will be compared to subjects without missing data.

10.5.9 Safety Data

An event that occurs during the treatment period will be considered a treatment-emergent AE if it was not present before the first dose of investigational product or was present before the first dose of investigational product and increased in severity during the treatment period. Adverse events (AEs) will be coded by primary system organ class and preferred term using the Medical Dictionary for Regulatory Activities (MedDRA).

The type of AE, number of events (n) and number (%) of subjects with events in each group will be tabulated. The type of AE, number of AEs and the number (%) of subjects with AEs will be presented by SOC, HLT, and preferred term. Subjects are counted once in each SOC, HLT, and preferred term. In addition, summaries of AEs by grouped causal relationship to treatment (all-cause/treatment-related) and grade will be provided by system organ class and preferred term.

The incidence of treatment-emergent AEs, on-therapy SAEs, and AEs leading to premature discontinuation will be summarized by preferred term and treatment group and will be sorted by decreasing frequency for the investigational product. In addition, the incidence of fatal on-therapy SAEs (i.e., events that caused death) will be summarized separately by treatment arm and preferred term. An SAE will be defined as an on-therapy SAE if it occurred during or after the infusion of investigational/placebo product.

Listings will be presented for subjects with SAEs, subjects with AEs leading to discontinuation, subjects with ESIs, and subjects who die (if any).

10.5.10 Clinical Laboratory Parameters and Vital Signs

Descriptive statistics for clinical laboratory values and changes from the baseline values at each assessment time point will be presented by treatment arm for each clinical laboratory parameter. Descriptive statistics for vital signs and changes from baseline values at each visit and at end of study will be presented by arm.

11 SOURCE DOCUMENTS AND ACCESS TO SOURCE DATA/DOCUMENTS

Each participating site will maintain appropriate research records for this trial, in compliance with §21 CFR 312.62, ICH E6, Section 4.9, and regulatory and institutional requirements for the protection of confidentiality of subjects. Each site will permit authorized representatives of the DMID, its designees, and appropriate regulatory agencies to examine (and when required by applicable law, to copy) clinical records for the purposes of quality assurance (QA) reviews, audits, and evaluation of the study safety and progress. These representatives will be permitted access to all source data and source documents, which include, but are not limited to, hospital records, clinical and office charts, laboratory notes, memoranda, subjects' memory aid or evaluation checklists, pharmacy dispensing records, recorded data from automated instruments, copies or transcriptions certified after verification as being accurate and complete, microfiches, photographic negatives, microfilm or magnetic media, x-rays, and participant files and records kept at the pharmacy, at the laboratories, and medico-technical departments involved in the clinical trial.

12 QUALITY CONTROL AND QUALITY ASSURANCE

Following a written DMID-accepted site quality management plan, each participating site is responsible for conducting routine QA and quality control (QC) activities to internally monitor study progress and protocol compliance. The site PI will provide direct access to all study-related source data/data collection forms, reports, training documentation, and regulatory files for the purpose of monitoring and auditing by the sponsor, and inspection by local and regulatory authorities. The site PI will ensure all study personnel are appropriately trained and applicable documentations are maintained on site.

The SDCC will implement QC procedures beginning with the data entry system and generate data QC checks that will be run on the database. Any missing data or data anomalies will be communicated to the participating site(s) for clarification and resolution.

13 DATA HANDLING AND RECORD KEEPING

13.1 Data Management Responsibilities

The investigator is responsible to ensure the accuracy, completeness, legibility, and timeliness of the data reported. All source documents should be completed in a neat, legible manner to ensure accurate interpretation of data. Black or blue permanent ink is required to ensure clarity of reproduced copies. When making changes or corrections, the original entry should be crossed out with a single line, and the change should be initialed and dated. DO NOT ERASE, OVERWRITE, OR USE CORRECTION FLUID OR TAPE ON THE ORIGINAL.

Data reported in the eCRF derived from source data collection forms/source documents should be consistent or the discrepancies should be explained.

13.2 Statistical and Data Coordinating Center/Biostatistician Responsibilities

Data collection is the responsibility of the study personnel at the participating clinical study site under the supervision of the site PI. During the study, the site PI must maintain complete and accurate documentation for the study.

The Emmes Company will serve as the SDCC for this study and will be responsible for data management, quality review, analysis, and reporting of the study data.

13.3 Data Capture Methods

Clinical (including, but not limited to, AE/SAEs/ESIs, concomitant medications, medical history, physical assessments, and clinical laboratory values) will be collected on data collection forms, as appropriate, by study personnel then entered into eCRFs via a 21 CFR Part 11-compliant internet data entry system provided by the SDCC. The data system includes password protection and internal quality checks, such as automatic range checks, to identify data that appear inconsistent, incomplete, or inaccurate.

All data collection forms/source documents (including laboratory reports) must be reviewed by the clinical team and data entry staff, who will ensure that the data are accurate and complete. Responses to QOL questionnaires will be collected on paper and entered by designated study staff into the eCRF for scoring and analysis. For additional details on data entry and reporting, refer to the MOP.

13.4 Types of Data

Data for this trial will include clinical, safety, QOL questionnaires, and outcome measures.

13.5 Study Records Retention

Study records and reports including, but not limited to, eCRFs, source documents, ICFs, laboratory test results, and study product disposition records will be retained for 2 years after a marketing application is approved for the study product for the indication for which it is being

investigated; or, if no application is to be filed or if the application is not approved for the study:product, until 2 years after the investigation is discontinued and the FDA has been notified.

These documents will be retained for a longer period; however, if required by local regulations. Informed consent forms (ICFs) for future use will be maintained as long as the sample/specimen exists.

No records will be destroyed without the written consent of the sponsor. It is the responsibility of the sponsor to inform the site PI when these documents no longer need to be retained.

